10 STATISTICAL ANALYSIS METHODS

10.1 Subject Disposition

The number of subjects screened, reasons for screen failure, and the number of subjects randomized will be summarized for all screened subjects. Number of subjects who complete and discontinue the study, and reasons for study discontinuation that occur post-randomization will be summarized by randomized treatment group (ie, placebo and gemcabene 600 mg) for the FAS. Reasons for discontinuation will be categorized using the reasons provided on the CRF (ie, AE, prohibited medication, non-compliance, withdrawal by subject, lost to follow-up, death, termination by sponsor, and other reasons). Additionally, protocol deviations will be listed for all randomized subjects.

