7.1.1 Full Analysis Set

The Full Analysis Set (FAS) comprises all randomized subjects who receive at least 1 dose of the study drug and have at least 1 post-baseline efficacy assessment. Subjects will be classified according to the treatment they were randomized to. Efficacy analyses will be conducted using the FAS.

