7.1.2 Per-Protocol Set

The Per-Protocol Set (PPS) includes all FAS subjects who complete the 12-week Treatment Period without major protocol deviations. Subjects will be classified according to the treatment they were randomized to. The PPS will be determined by the sponsor prior to treatment unblinding at the end of the study. The PPS will be used to assess the robustness of analysis results. Subjects excluded from the PPS and the reason for exclusion will be provided in the listings.

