9.6 Visit Windows

Visit windows will be used to classify scheduled (except the Follow-up Visit), unscheduled, and early termination (ET) visits according to [Table 2](#). below to ensure that all visits have the potential to contribute to summaries. If 2 or more visits occur within the same analysis window, data from the visit closest to the target day will be used in summaries and/or analysis; if the visits are the same distance from the target day, data from the later date will be used. Data for laboratory parameters scheduled to be measured post-randomization at only the Week 12 or ET Visit (ie, HbA1c, C1 hsCRP, SAA, fibrinogen, adiponectin, FPG, and insulin) will be summarized under the Week 12 Visit. If there is more than one value, the latest will be used. For efficacy, parameters measured after last dose + 2 days will not be considered. Except for adverse events, for safety, parameters measured after last dose + 5 days will not be considered.

Table 2. Visit Windows for Assessments Done at Day 1, Weeks 2, 4, 8, and 12^a

Visit	Target Study Day	Visit Window
Day 1	1	(1)
Week 2	15	(2, 22)
Week 4	29	(23, 43)
Week 8	57	(44, 71)
Week 12	85	> 71

^a. As Apo and select urinalysis parameters are not measured at Week 2, the Visit Window for Week 4 for Apo and urinalysis parameters is (2, 43). Remaining urinalysis parameters are not measured at Week 2 or Week 8; thus, the Visit Windows for Week 4 and Week 12 are (2, 57) and > 57, respectively.

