10.3.2 Treatment Exposure

Duration of exposure will be calculated for each subject as (last dose date – first dose date + 1) and will be summarized using descriptive statistics. The number of subjects who receive ≥ 1 day, ≥ 7 days, ≥ 14 days, ≥ 28 days, ≥ 42 days, ≥ 56 days, ≥ 70 days, and ≥ 84 days of the study medication will be presented by actual treatment group for the SAS.

Days on treatment will be computed as the number of days that the study medication was taken (ie, treatment exposure excluding days when the study medication was interrupted). Number of days on treatment and number of days study medication was interrupted for will be summarized for the SAS.

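### SAP 10.1 tabulates disposition by arm for the FAS only, so it may omit randomized subjects who left before a dose or any post-baseline efficacy value

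*SAP*

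**What the plan says.** SAP 10.1 covers disposition in three parts.

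- **All screened subjects.** "The number of subjects screened, reasons for screen failure, and the number of subjects randomized will be summarized for all screened subjects". This part stops at the number randomized.
- **FAS, by randomized arm.** Completers, discontinuations and reasons are tabulated here: "reasons for study discontinuation that occur post-randomization will be summarized by randomized treatment group (ie, placebo and gemcabene 600 mg) for the FAS". The reasons are those on the CRF: "AE, prohibited medication, non-compliance, withdrawal by subject, lost to follow-up, death, termination by sponsor, and other reasons".
- **All randomized subjects.** The only output is a listing: "protocol deviations will be listed for all randomized subjects".

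SAP 7.1.1 says the FAS "comprises all randomized subjects who receive at least 1 dose of the study drug and have at least 1 post-baseline efficacy assessment".

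Four other planned outputs bear on the point.

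- SAP 7.1 promises a table of the number of subjects in each analysis population. It does not say that the table is by arm, and it mentions no reasons.
- SAP 7.1.2 adds that "Subjects excluded from the PPS and the reason for exclusion will be provided in the listings".
- SAP 12 and 12.1 report treatment-emergent adverse event (TEAE) discontinuations and deaths by treatment group on the Safety Analysis Set, which requires only a dose.
- SAP 10.3.2 gives counts by duration of exposure that "will be presented by actual treatment group for the SAS", where SAS is the Safety Analysis Set.

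Protocol 4.3 requires the reason for withdrawal to be recorded in the eCRF. Protocol 6.6 includes a fasting lipid panel at the Early Termination (ET) visit.

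**The concern.** A disposition table should account for everyone randomized. This one is restricted to subjects who stayed long enough to be dosed and to give a post-baseline efficacy value. A subject who withdraws consent or is lost to follow-up before then is a discontinuation that the discontinuation table cannot show.

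The primary ANCOVA uses the same set. A reader who wants to know whether exclusion from the primary analysis was balanced between arms, and why it happened, would look first at this table, but the table has the same exclusion built in. At stake are a by-arm discontinuation rate that may be printed too low, possibly by different amounts in the two arms, and reasons for leaving that are not tabulated by arm.

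**Working it through.** **1. Where each reason is tabulated by arm**

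| Subjects | AE | Death | Other six CRF reasons |
|---|---|---|---|
| In the FAS | SAP 10.1 | SAP 10.1 | SAP 10.1 |
| Dosed, not in the FAS | SAP 12.1 (TEAE discontinuations) | SAP 12.1 | No table |
| Randomized, never dosed | No table | No table | No table |

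SAP 10.1 names 8 CRF reasons. For dosed subjects outside the FAS, 2 are covered by SAP 12.1, leaving 8 − 2 = 6: prohibited medication, non-compliance, withdrawal by subject, lost to follow-up, termination by sponsor, and other.

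**2. What can be recovered indirectly**

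- Overall dropout: number randomized (all-screened summary) minus completers (FAS table), taking every completer to be in the FAS. With 10 dropouts of 104, this is 1 − 94/104 = 9.6%, however many are omitted.
- Dosed subjects outside the FAS, per arm: Safety Analysis Set N minus FAS N. The first is by actual treatment and the second by randomized treatment, so this works if no one received the wrong treatment.
- Individual subjects: every non-FAS subject is also outside the Per-Protocol Set, so the exclusion listing should show each one with a reason. It is a listing, not a table.

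**3. The planned dropout, as a scale**

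The inputs are in SAP 9.1: difference 17, SD 20, two-sided α = 0.05, power 80%, dropout 10%.

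- Standardized difference: 17/20 = 0.85.
- Two-sample t-test: 22.73, so 23 evaluable per arm per stratum (power 80.5%).
- Dropout inflation: 23/0.90 = 25.6, so 26.
- Total: 26 × 4 = 104, or 52 per arm.

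The plan's figure reproduces. Ten percent of 52 is 5.2, so about 5 dropouts per arm.

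**4. Effect on the printed rate**

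The documents do not say how many leavers would fall outside the FAS, so the number omitted, k, is an assumption. With 5 true dropouts of 52, the printed rate is (5 − k)/(52 − k).

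| k omitted | Printed rate |
|---|---|
| 0 | 5/52 = 9.6% |
| 1 | 4/51 = 7.8% |
| 2 | 3/50 = 6.0% |
| 3 | 2/49 = 4.1% |
| 4 | 1/48 = 2.1% |
| 5 | 0/47 = 0.0% |

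At the low end the rate falls by about 1.8 points per omitted subject. The last row would need every leaver to go without a post-baseline value, which nothing in the documents suggests. If one arm lost none and the other lost 2, arms with the same true dropout would print 9.6% and 6.0%.

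**5. Why k is probably small**

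Randomization and the first on-site dose occur at the same Day 1 visit (Protocol 6.4.1), so never-dosed subjects should be very few. The first scheduled post-baseline lipid panel is at Day 15 ± 3, that is Day 12 to 18 (Protocol 6.4.2). A subject who leaves before then can still enter the FAS through the ET lipid panel, which Protocol 4.3 asks staff to try to obtain.

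**The case against.** The documents do not contradict themselves here. The protocol names no population for a disposition table, and what it does require by treatment group (deaths and withdrawals due to adverse events) is delivered on the Safety Analysis Set. The printed percentage is correct for the FAS, and is low only relative to all randomized subjects. Overall dropout and, normally, the per-arm count of dosed non-FAS subjects can be derived, and the excluded subjects should appear in a listing. All of this stands and is why the point is minor. It does not put the missing reasons into a by-arm table.

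Three stronger readings are tempting, and the documents do not support them.

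- *The earliest leavers are omitted.* Some may be. Those with an ET lipid panel can enter the FAS, so there may be none.
- *All reasons other than adverse events are lost.* Deaths of dosed subjects are counted by arm in SAP 12.1.
- *A late ET sample keeps a subject out of the FAS.* SAP 9.6 says "For efficacy, parameters measured after last dose + 2 days will not be considered", and the ET visit has no stated day relative to the last dose. However, SAP 7.1.1 sets no on-treatment condition for FAS entry and does not say whether such a value counts. Read literally, it would. Only on the other reading would a subject who stops before Week 2 and is sampled 3 or more days after the last dose be left out. That is a separate ambiguity, and the point does not depend on it.

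**Conclusion.** The point holds as a low-severity reporting correction. By its stated population, the by-arm table in SAP 10.1 excludes any randomized subject without a dose or a post-baseline efficacy assessment. For such subjects, no by-arm table gives six of the eight reasons if they were dosed, or any reason if they were not.

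The number affected is unknown. Under the assumption of 5 dropouts of 52 in an arm, omitting 1 or 2 lowers the printed rate from 9.6% to 7.8% or 6.0%. A difference between arms in the number omitted is possible, but nothing in the documents shows one.

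A reader might also infer that the primary result is biased or underpowered. That does not follow: this concerns a descriptive table, and the ANCOVA, power and sample size are unchanged.

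**What to change.** In SAP 10.1, change the population for the completion, discontinuation and reasons summary from the FAS to all randomized subjects, the set that section already uses for the protocol-deviation listing. Show by randomized arm the numbers randomized, dosed, completing, and discontinuing for each CRF reason. A row for the number in the FAS may be added, but that row depends on how FAS entry is read when the only post-baseline sample is late.

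The cost is a short wording change and a few more table rows. No new data are needed, since Protocol 4.3 already requires the withdrawal reason in the eCRF. The reported discontinuation rate may be slightly higher. If no one is outside the FAS, the completion and reason counts stay the same.

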10.2 Demographics and Baseline Characteristics

Demographic information will be summarized using descriptive statistics by randomized treatment group and overall for the FAS. Additionally, demographic information will be presented by statin-intensity stratum (moderate and high), for diabetic subjects, and for subjects with and without mixed dyslipidemia. Explicitly, the following characteristics will be summarized:

- Sex (Male, Female);
- Menopausal Status for Females (post-menopausal or surgically sterile, pre-menopausal);
- Race (White, Black or African American, Asian, American Indian or Alaska Native, Native Hawaiian or Other Pacific Islander, Other);
- Ethnicity (Hispanic or Latino, Not Hispanic or Latino, Unknown);
- Age;
- Height;
- Weight; and
- BMI,

where age will be computed for each subject using the following formula:

$$\text{Age} = \text{integer} ([\text{Screening Visit date} - \text{date of birth}] / 365.25),$$

and BMI will be calculated using the following formula:

$$\text{BMI} = (\text{body weight in kilograms}) / (\text{height in meters})^2.$$

Pregnancy test results will be listed for female subjects.

Additionally, baseline primary and secondary endpoints along with 1 exploratory endpoint, C1 will be summarized for the FAS by randomized treatment group and overall. Specifically, the following parameters will be summarized at baseline: lipids, apolipoproteins, inflammatory biomarkers, and the Framingham Risk Score. This table will then be repeated for

each baseline statin-intensity stratum (moderate, high). Additionally, the number and percentage of diabetic subjects and subjects on and not on ezetimibe in each of the previously mentioned groups will be summarized for the FAS. A subject on ezetimibe is defined as a subject with ezetimibe recorded on the Concomitant Medications CRF with a start date on or before first dose (ie, medication start date \leq day of first dose) and a stop date on or after first dose (ie, medication stop date \geq day of first dose). Partial and missing dates will be imputed using rules in [Appendix 2](#).

Further, for the subgroup of diabetic subjects within the FAS, baseline fasting insulin, FPG, HbA1c, lipids, apolipoproteins, and inflammatory biomarkers will be summarized by randomized treatment group and overall.

Lastly, for the subgroup of subjects with mixed dyslipidemia at baseline within the FAS, baseline lipids, apolipoproteins, and inflammatory biomarkers will be summarized by randomized treatment group and overall. This table will then be repeated for the subgroup of subjects without mixed dyslipidemia at baseline within the FAS.

For categorical parameters, denominators for percentages will be the number of subjects in the corresponding group (eg, gemcabene 600 mg) with non-missing data for the parameter of interest.

10.3 Treatment Compliance and Exposure

10.3.1 Treatment Compliance

Compliance with administration of study drug will be assessed at each study visit post-randomization during the Treatment Period and at the ET Visit, if applicable, and recorded on the appropriate CRF and the drug accountability log. Compliance will be computed using information collected on the Study Drug Interruption CRF. Specifically, compliance will be calculated for each subject at each scheduled post-randomization visit during the treatment period (and the ET visit, if applicable), where treatment period is defined as the time period bounded by the first dose date and last dose date, as $(\text{number of tablets taken since last visit} / \text{number of tablets that should have been taken since last visit}) * 100$. As each subject is instructed to take 3 tablets per day during the treatment period, the number of tablets that should have been taken since the last visit will be computed as $3 \text{ tablets per day} * \text{number of days since last visit}$, where the number of days since the last visit will be computed as $(\text{day of visit} - \text{day of last visit} + 1)$. Compliance will be summarized by visit and actual treatment group for the SAS.

For each subject, overall compliance will be computed as $(\text{number of tablets taken during treatment period} / \text{number of tablets that should have been taken during treatment period}) * 100$. The number of tablets that should have been taken during the treatment period will be computed as $3 \text{ tablets per day} * \text{number of days during the treatment period}$, where the number of days during the treatment period will be computed as $(\text{last dose date} - \text{first dose date} + 1)$. Subjects will then be grouped into categories of overall compliance ($< 80\%$, 80% to 100%) according to their overall estimate of compliance. Overall compliance and categories of compliance will be summarized using descriptive statistics by actual treatment group for the SAS.

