10.1.5 Data Validation

Validation checks programmed within the EDC system, as well as supplemental validation performed via review of the downloaded data, will be applied to the data in order to ensure accurate, consistent, and reliable data. Data identified as erroneous, or data that are missing, will be referred to the investigative site for resolution through data queries.

The eCRFs must be reviewed and electronically signed by the Investigator.

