9.4 Handling of Missing Data

Missing values at baseline will not be imputed in any situation. For efficacy analyses, values missing post-randomization will be imputed using LOCF (unless otherwise specified); only post-randomization values on treatment will be used for imputation. For example, if a subject has Week 12 efficacy parameters measured more than 2 days after their last dose, their Week 12 efficacy values will be imputed using the last non-missing value while on treatment (eg, Week 8). The imputed values will be used in summaries and analysis. For safety analyses, observed case data will be used.

Imputation will not be conducted for AEs missing severity or relationship to study medication. AEs missing severity will be excluded from summaries of AEs by severity. Adverse events missing relationship will be excluded from summaries of related AEs.

Rules for partial and missing dates for prior and concomitant medications and smoking status are given in [Appendix 2](#).

Drug interruptions with partial start and/or stop dates will be assumed to be 1 day in length, and will be assumed to have occurred in the visit interval prior to when the interruption was collected (eg, if a drug interruption with partial dates was collected at the Week 8 visit, we will assume that the interruption occurred between the previous visit [eg, Week 4] and the Week 8 visit).

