Appendix 2. Prior and Concomitant Medications and Smoking Status Date Imputation

Imputation Rules for Partial Dates (D = day, M = month, Y = year)			
Parameter	Missing	Additional Conditions	Imputation
Start date	D only	M and Y same as M and Y of first dose of study drug	Date of first dose of study drug
		M and/or Y not same as date of first dose of study drug	First day of month
	M and D	Y same as Y of first dose of study drug Y not same as Y of first dose of study drug	Date of first dose of study drug Use Jan 01 of Y
	M, D, and Y	None - date completely missing	Day prior to date of first dose of study drug
Stop date	D only	M and Y same as M and Y of last dose of study drug	Date of last dose of study drug
		M and/or Y not same as date of last dose of study drug	Last day of month
	M and D	Y same as Y of last dose of study drug Y not same as Y of last dose of study drug	Date of last dose of study drug Use Dec 31 of Y
	M, D, and Y	None - date completely missing and NOT ongoing	Date of last dose of study drug

Note: In all cases, if an estimated start date is after a complete stop date, use the first day of the stop date month.

Similarly, if the estimated stop date is before a complete or imputed start date, use the last day of the start day month.

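### By-visit compliance counts Days 15, 29 and 57 twice (88 days against 85), and every partial-date interruption is set to 1 day even where recorded dates show longer; descriptive tables only

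*SAP*

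**What the plan says.** **By-visit compliance.** SAP 10.3.1 divides tablets taken since the last visit by tablets expected since the last visit. The expected number is 3 per day times a day count, "where the number of days since the last visit will be computed as" visit day minus previous visit day plus 1. The rule applies at every scheduled post-randomization visit and at an early termination (ET) visit. The section also limits the calculation to the treatment period, "where treatment period is defined as the time period bounded by the first dose date and last dose date".

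**Overall compliance.** The same section uses 3 tablets per day times the days in the treatment period, "where the number of days during the treatment period will be computed as" last dose date minus first dose date plus 1. Only this overall figure is split into the classes below 80% and 80% to 100%.

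**Source of the numerator.** "Compliance will be computed using information collected on the Study Drug Interruption CRF". The section does not say over which days the tablets taken since the last visit are counted.

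**Partial dates.** SAP 9.4 states: "Drug interruptions with partial start and/or stop dates will be assumed to be 1 day in length". It places that day in the visit interval before the visit at which the interruption was collected. The length also feeds SAP 10.3.2: "Number of days on treatment and number of days study medication was interrupted for will be summarized for the SAS".

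**Data queries.** Protocol 10.1.5 provides for missing data to go back to the site first: "Data identified as erroneous, or data that are missing, will be referred to the investigative site for resolution through data queries".

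**The concern.** Adding 1 is right for a single period with both ends included. It is not right for a chain of adjoining periods, because each intermediate visit day closes one interval and opens the next. The by-visit figures then do not agree with the overall figure in the same section. Because the numerator window is not defined, two programmers could produce different tables from the same data.

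The 1-day rule is a separate matter. It makes no exception for an interruption whose recorded date parts already show that it lasted longer. Every real interruption lasts at least 1 day, so the error can go in one direction only, toward better adherence.

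At stake is whether the descriptive compliance and exposure tables for the Safety Analysis Set can be read at face value.

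**Working it through.** **Inputs.** Target visit days are 1, 15, 29, 57 and 85 (SAP 9.6, Table 2). The treatment period is Day 1 to Day 85 inclusive (SAP 6.1, Table 1). The dose is 3 tablets per day (SAP 10.3.1).

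**1. The plan's own figure.** Overall formula: 85 − 1 + 1 = 85 days, or 3 × 85 = 255 tablets. This matches the stated treatment period.

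**2. By-visit formula as written.**
- Week 2: 15 − 1 + 1 = 15
- Week 4: 29 − 15 + 1 = 15
- Week 8: 57 − 29 + 1 = 29
- Week 12: 85 − 57 + 1 = 29
- Sum: 88 days, or 3 × 88 = 264 tablets

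Four intervals add 1 four times where the whole period needs it once. With the last dose on the Week 12 visit day, the excess is therefore 3 days for any visit timing within the windows.

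**3. Effect if tablets taken are counted over the same inclusive days.** Full adherence reads 15/15 or 29/29 = 100%.
- With m missed days, none on a shared visit day, a 14-day interval treated as 15 days reads too high by m/14 − m/15 = m/210. A 28-day interval treated as 29 reads too high by m/28 − m/29 = m/812. One missed day gives 0.5 or 0.1 points; seven missed days give 3.3 or 0.9 points.
- A dose missed only on Day 15 (assumed) gives 14/15 = 93.3% at both Week 2 and Week 4. With non-overlapping intervals that start on the visit day, it gives 14/14 = 100% at Week 2 and 13/14 = 92.9% at Week 4.
- An interruption on Days 13–17 (assumed, 5 days) counts as 3 + 3 = 6 missed days. Week 2 reads 12/15 = 80.0% instead of 12/14 = 85.7%.

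**4. Effect if each tablet is counted once.** A fully adherent subject reads as follows.
- Visit-day dose assigned to the interval that ends: 15/15, 14/15, 28/29, 28/29 = 100%, 93.3%, 96.6%, 96.6%.
- Visit-day dose assigned to the interval that starts: 14/15, 14/15, 28/29, 29/29 = 93.3%, 93.3%, 96.6%, 100%.

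Which visits carry the excess therefore depends on this convention.

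**5. ET visit after the last dose.** Assumed dates: Week 4 visit on Day 29, last dose on Day 40, ET visit on Day 45. The formula gives 45 − 29 + 1 = 17 days. Stopping at the last dose, as the section's own bound implies, gives 40 − 29 + 1 = 12.

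**6. The 1-day rule.** One interruption of true length L in an 85-day period, set to 1 day, is reported as 84/85 = 98.8%, whatever L is. The true value is (85 − L)/85.
- L = 17: 68/85 = 80.0%, class unchanged.
- L = 18: 67/85 = 78.8%, the first length at which the class is wrong.
- The threshold falls with a shorter treatment period: 17 days for an 82-day period (65/82 = 79.3%) and 12 days for a 57-day period (45/57 = 78.9%).

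Illustration (assumed dates): start 10 May, stop recorded only as June. The shortest possible length is 23 days to 1 June inclusive, or 22 if the stop date is the day dosing resumes. True compliance is then at most 62/85 = 72.9% or 63/85 = 74.1%, against 98.8% reported. An interruption of 22 days also cannot fit within the single 14-day interval before Week 2 or Week 4, so the placement rule fails as well.

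**The case against.** The case for leaving the text alone has several sound parts.

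- **Nothing reports 88.** The SAP never adds up the by-visit intervals. Overall compliance and the 80% classes use the correct 85-day formula. If the numerator covers the same inclusive days, a fully adherent subject still shows 100%. This stands and limits the size. It does not remove the overlap, because a visit-day dose is mis-weighted on either reading of the numerator.
- **The ET visit.** A programmer could take the bound at the last dose as an instruction to truncate. That is fair: the wording conflicts, and a wrong value is not certain.
- **The 1-day rule is deliberate.** The SAP document history lists it under Amendment 1.0, and site queries come first. Packaging is also returned at each visit (Protocol 5.5.5), and accountability logs hold dates and quantities (Protocol 5.5.6). The form's layout is not in the documents, so the May–June case is hypothetical. All this bears on how often the rule is used. It does not justify a length that recorded date parts contradict.
- **Appendix 2 is no template.** It does use a known month and year, for example where a stop date has "M and/or Y not same as date of last dose of study drug" and takes the last day of that month. But it is written for medications and smoking. A start date lacking only its day, in the month of first dose, would become the first-dose date, which is a poor choice for an interruption. Its absence from SAP 9.4 is not an inconsistency.

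A reader might infer that the primary result or the Per-Protocol Set is affected. The documents do not support that. The primary ANCOVA and its LOCF rule do not use these compliance figures, and SAP 7.1.2 sets no compliance cut-off.

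**Conclusion.** Both rules are wrong as written, and the consequence is minor and descriptive.

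The overlap affects by-visit compliance only. Its size depends on the undefined numerator: no shift for full adherence and m/210 or m/812 for missed days away from the shared visits, or 93.3% and 96.6% for a fully adherent subject if each tablet is counted once. It would go too far to say that adherent subjects will be shown below 100%, since the text also allows the other count. No single range of percentage points describes the shift, because it grows with the number of missed days and can change direction when a shared day is missed.

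The 1-day rule can only overstate overall compliance and days on treatment, and understate days interrupted. It puts an 85-day completer with one such interruption in the wrong class only from 18 days. How many interruptions keep partial dates after queries is unknown and may be zero, so no actual misclassification can be claimed.

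The 88-day total assumes nominal visits and a last dose at Week 12. The interruption and ET dates used above are assumptions.

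**What to change.** **SAP 10.3.1.** Use non-overlapping intervals: visit day minus previous visit day. End the last interval at the last dose date and count that day once. On visit days, drug is taken after blood sampling (Protocol 5.5.4), so the visit-day dose belongs to the interval that follows. At nominal timing this gives 14 + 14 + 28 + 29 = 85, equal to the overall formula, and it also holds when an ET visit falls after the last dose. State that tablets taken are counted over the same days.

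**SAP 9.4.** Keep 1 day only where the known date parts allow it. Otherwise use the shortest length consistent with them, assign those days to the visit intervals they cover, and report how many interruptions had an imputed length. That count would show the reader whether the rule mattered.

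**Cost.** Two SAP sentences and minor programming, with no change to any efficacy output. The minimum length still leans toward better adherence, though less than a flat 1 day. Reported overall compliance may be slightly lower than under the current rule for any affected subject.
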